#### 10.4 Subgroup analyses

Within the Toric IOLs group, a subgroup of participants presented with post-surgery IOL rotation > 5 degree will be isolated to compare the outcomes. This subgroup of participants is very likely to need

Vision and balance changes after bilateral implantation of Toric IOLs  
IRAS ID: 286913

another adjustment surgery. Their data will inform the impact of IOLs rotation on surgery complications and whether such rotation may be related to degree of astigmatism.

In both the Toric IOLs and non-Toric IOLs group, subgroups of different degree of astigmatism: mild (<1.50), moderate (1.5-3.0) and severe (3.0+) will be differentiated to compare the outcomes to help inform if Toric IOLs offer similar beneficial effect across cataract patients with wide range of astigmatism. This will help to identify which patients should be referred for Toric IOLs and support evidence-based practice.

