### Risks

For Toric IOLs to correct astigmatism, they need to be placed specifically with reference to the steepest meridian of the eye. All IOLs can rotate, but rotation of Toric IOLs can affect its astigmatism correction effect. Small rotations do not affect the astigmatic power, but larger rotations will reduce the astigmatism correcting effect. If the IOL is rotated 30 degrees, the astigmatism correcting effect is eliminated (Visser et al., 2013). In approximately 1% of patients, the Toric lens rotates significantly reducing the level of astigmatism that is corrected by the Toric lens. If this is the case, and the participant is unhappy with their visual outcome, the surgeon will discuss the possibility of a secondary procedure to reposition the lens. The surgeon will discuss the risks of the repositioning procedure with the participant to determine if the benefits outweigh the risks. It is important to note that this repositioning (to correct any unwanted astigmatism) is only possible with Toric lenses, with standard IOLs unwanted astigmatism will not be corrected. Even with significant Toric IOLs rotation, additional surgery is generally not required as by removing the cataract, the rotated Toric IOLs still provide significant improvement in vision and the remaining astigmatism can be corrected with spectacles.

The mobility assessment involves walking over obstacles, turning, going up and down stairs. The participants will have three small portable motion sensors placed on their neck and lower back and will be asked to wear a pair of eye tracking glasses during the mobility tasks. There is a very low risk of falls, similar as during any normal activities of daily living. The risk will be minimal as all assessment will be carried out under the supervision of an experienced physiotherapist. Also, the assessment venues are part of the University campus which is regularly controlled to maintain environmental safety and has provision of first aid equipment. A patient and public involvement discussion has been conducted which covered discussion about assessments and the research design. All participants were supportive about the research idea and felt the research could raise awareness of available choice of IOLs. Participants were asked about the practicality of the research and felt it would be better to have all assessments done in one site. The assessments were to be conducted at Marjon Biomechanics Lab and

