#### Post-operative complications:

- endophthalmitis (inflammation of the internal eye tissues, most commonly caused by an infection) and bleeding.
- irregular astigmatism
- dry eye
- keratectasia (progressive myopia, irregular astigmatism, ghosting, fluctuating vision and problems with scotopic vision. The progression leads to severe loss of corrected visual acuity)
- Patient reported subjective complaints of halos, glare, and ghost images.
- Wound leak
- Flat anterior chamber
- Hyphema
- Vitreous in anterior chamber
- Vitreous in wound

Vision and balance changes after bilateral implantation of Toric IOLs  
IRAS ID: 286913

- Raised IOP
- Pupillary block
- Anterior synechiae
- Posterior synechiae
- Deposits on IOL
- Fibrin in Pupil
- Nuclear remnants
- Cortical Remnants
- Retinal detachment
- Cystoid macular oedema
- Anterior capsular Opacification
- Posterior capsular opacification
- Intraocular lens tilt and decentration
- Cells/flare in the anterior chamber

Toric IOLs have a few other potential complications. Astigmatism may be overcorrected or under-corrected.

As mentioned previously, the Toric IOL may rotate off-axis. There will be some partial effect if it rotates off-axis. For example, the correction effect of the Toric IOLs is reduced by 10% for every 3° rotation off-axis. For the lens to lose its full effect, it would have to be off axis by 30°. Prevention of IOL rotation includes complete removal of Ophthalmic Viscosurgical Devices (OVDs), especially posterior to the IOL.

Most patients do extremely well following this surgical technique. The technical surgical learning curve for the surgeon is minimal for an outcome that is reliably predictable. Toric IOLs, exclusively or in conjunction with astigmatic keratotomy and/or strategic cataract incision placement, can result in excellent management of astigmatism.

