## **10. STATISTICS AND DATA ANALYSIS**

### **10.1 Sample size calculation**

Sample size test calculation was carried out with the G\*Power 3.1 program (Faul *et al.*, 2007) for comparison of the main outcome measure of dynamic balance (between IOL design) using mixed ANOVA (repeated measures, between factor being the type of IOL).

Based on of the dynamic balance measurement (JERK score) in a previous study (Mancini *et al.*, 2011) an estimated medium effect size (0.25) will be used. With a power of 85% and level of significance ( $p$ ) set at 0.05 and effect size of 0.25, 55 participants will be required in each group (Monofocal vs Toric IOL). Accounting for a 20% drop out rate, 70 participants will therefore be recruited in each group (A total of 140 participants).

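### Sections 10.4 and 2.1 conflict on whether rotated Toric lenses lead to further surgery, and the >5 degree split, of unknown size, is the only planned analysis of rotation against outcome

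*Combined protocol and SAP*

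**What the plan says.** Section 10.4 defines the group within the Toric arm: "a subgroup of participants presented with post-surgery IOL rotation > 5 degree will be isolated to compare the outcomes". It then says "This subgroup of participants is very likely to need" another adjustment operation. It expects these data to show how rotation bears on surgical complications and whether rotation goes with the degree of astigmatism.

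Section 2.1 (Risks) gives the only rotation rate in the documents: "In approximately 1% of patients, the Toric lens rotates significantly". It makes a second operation conditional: if "the participant is unhappy with their visual outcome, the surgeon will discuss the possibility of a secondary procedure to reposition the lens". It adds: "Even with significant Toric IOLs rotation, additional surgery is generally not required". On the size of the effect, 2.1 says "Small rotations do not affect the astigmatic power, but larger rotations will reduce the astigmatism correcting effect", and 9.5 says "the correction effect of the Toric IOLs is reduced by 10% for every 3° rotation off-axis".

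Section 10.3.3 lists rotation, for the Toric group only, as interval data to be summarised by averages and Bland-Altman agreement. It does not relate rotation to any outcome. Section 3.5 names two rotation measures, one from the intended position and one from the steepest meridian. Section 10.4 does not say which of them the 5 degree cut-off uses, at which visit, or whether it applies to an eye or to a participant.

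**The concern.** There are two linked problems.

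First, the analysis section and the risk assessment describe the consequence of rotation in opposite terms. A reader of 10.4 would expect most of the subgroup to return to theatre; a reader of 2.1 would expect few to. Anyone interpreting the subgroup, or judging the risk described to participants, needs one account.

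Second, 10.4 asks graded questions (what rotation does, and whether it varies with astigmatism) but answers them by a cut at 5 degrees. No expected number above the cut is given. If few participants exceed it, the comparison cannot answer either question. The cut also treats 0 and 5 degrees alike, although the degrees will have been recorded.

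**Working it through.** **1. The statements side by side.** Section 10.4 calls further surgery very probable above 5 degrees. Section 2.1 says it is usually unnecessary even when rotation is significant.
- If the two thresholds coincide, the statements are opposite.
- If more than 5 degrees is the milder condition, 10.4 is harder still to square with 2.1.
- Only if *significant* began below 5 degrees could both stand. By 9.5, the loss at 5 degrees is 5/3 × 10% = 16.7%, and total loss comes at 30 degrees (30/3 × 10% = 100%). That reading would make *significant* start at a loss under about 17%, and nothing in 2.1 says so.

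**2. The plan's sample size.** Section 10.1 gives f = 0.25, 85% power, alpha 0.05 and 55 per group. For the between-group test in a repeated-measures ANOVA, λ = f²·N·m / (1 + (m − 1)ρ). Assuming m = 2 measurements and ρ = 0.5 (neither is stated), N = 110 gives λ = 0.0625 × 110 × 2 / 1.5 = 9.17 and power 0.851, so the stated figure is reproduced. Dropout: 110 / 0.8 = 137.5, or 138 (69 per group), which the plan rounds to 70. The Toric arm is therefore 70 recruited and 55 evaluable.

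**3. Expected size of the subgroup** (n × rate). Only the 1% comes from the documents, and there it refers to undefined significant rotation. The other rates are assumptions.

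| Rate per patient | Of 70 | Of 55 |
|---|---|---|
| 1% (from 2.1, if it applied) | 0.70 | 0.55 |
| 5% (assumed) | 3.5 | 2.75 |
| 10% (assumed) | 7 | 5.5 |
| 20% (assumed) | 14 | 11 |

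At 1% of 70, P(0) = 0.99⁷⁰ = 0.495 and P(1) = 70 × 0.01 × 0.99⁶⁹ = 0.350, so P(0 or 1) = 0.845.

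**4. What a split could detect.** For 80% power at two-sided 0.05, the normal approximation is d = (1.960 + 0.842) × √(1/n₁ + 1/n₂). The t-based value follows in brackets.
- 2 v 68: 2.802 × 0.717 = 2.01 (2.04)
- 7 v 63: 2.802 × 0.398 = 1.12 (1.13)
- 14 v 56: 2.802 × 0.299 = 0.84 (0.85)

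For comparison, f = 0.25 with two equal groups is d = 2 × 0.25 = 0.5.

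**5. What a continuous predictor could detect.** With one value per Toric participant, r = tanh(2.802 / √(n − 3)). For n = 70 this is tanh(0.342) = 0.33; for n = 55 it is tanh(0.389) = 0.37. This does not depend on how many participants exceed 5 degrees, but it does need rotation to vary.

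**The case against.** The best defence is that little hangs on this. The sentence in 10.4 about further surgery is descriptive: it triggers no procedure, test or stopping rule. The subgroup is not part of the primary analysis. Section 10.3.3 already keeps rotation as interval data. The documents give no rate above 5 degrees, so the subgroup cannot be shown to be small. If nearly all lenses stay close to their axis, a continuous analysis will also be uninformative.

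Most of that stands, and it limits the weight of the point. It does not remove the conflict, which needs no outside figure. Nor does it give 10.4 a workable analysis: the averages and Bland-Altman plots of 10.3.3 describe where the lenses sit, not what rotation does to outcome. The missing rate is itself a reason not to rest the only such analysis on a cut-off of unknown yield.

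A further fair objection concerns the form of any replacement. Dynamic stability, the falls scales and CAT-PROM5 have one value per participant per visit. A model that entered both eyes for those outcomes would count each value twice. The replacement must therefore separate eye-level from participant-level outcomes.

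**Conclusion.** The conflict between 10.4 and 2.1 is real and the passages must be reconciled. This review does not say which clinical statement is right. Separately, the split above 5 degrees is the only planned link between rotation and outcome or degree of astigmatism, and its size is unknown. It could be nearly empty at the one rate in the documents. At an assumed 20% (14 of 70) it would still need a difference of about 0.85 standard deviations. This is a minor, nearly free improvement to an exploratory analysis.

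A reader might infer more than the documents support:
- **That the subgroup will hold about one participant.** This borrows the 1% in 2.1, which is not tied to 5 degrees. Since 5 degrees is only about a 17% loss by 9.5, the group could be much wider; 0.6 to 0.7 is a low-end case. Applying the 1% to eyes changes the unit, because 2.1 speaks of patients.
- **That 2.1 understates the risk of further surgery.** This follows only if 10.4 is the correct statement, which the documents do not settle.
- **That the 1% rate and the 9.5 figure are part of the contradiction.** They are compatible with each other and with either statement about surgery.
- **That the plan throws the measured degrees away.** Section 10.3.3 summarises them; what is missing is their use to explain outcome.

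**What to change.** 1. Reconcile 10.4 with 2.1 on what rotation above 5 degrees implies. State in degrees what 2.1 means by *significant*, and how often rotation above 5 degrees is expected.
2. In 10.4, make the main exploratory analysis within the Toric arm a regression on absolute rotation in degrees as a continuous variable. Name which of the two measures in 3.5 is used, and the visit.
3. For eye-level outcomes (residual astigmatism, monocular acuity), and for the relation of rotation to pre-operative astigmatism, use all Toric eyes with a participant effect.
4. For participant-level outcomes (dynamic stability, falls scales, CAT-PROM5), use one rotation value per participant at visit 3, such as the larger or the mean absolute rotation of the two eyes. By 7.7 and 8.6, the second eye may not have been operated on at visit 2.
5. List eyes above 5 degrees descriptively, with complications and any further surgery. This keeps the complications question of 10.4 without a test.

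The cost is some wording and one extra exploratory model on data already planned for collection. Its limitation should be stated: if nearly all rotations are small, it will carry limited information.

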### **10.3 Statistical analysis plan**

All data will be assessed for normality using a combination of assessing histogram plots and the Shapiro-Wilks Normality Test. Descriptive summary statistics for outcome measures relating to vision (acuity and refraction) will be recorded as mean +/- standard deviation.

Mixed ANOVA and post-hoc Bonferroni tests will be used to determine the statistical differences in the baseline characteristics and outcome measures between the Toric monofocal IOLs group and the non-Toric monofocal IOLs group. The between-subjects factor would be type of IOL lens and the within-subjects factor would be time (pre-surgery vs post-surgery). Level of significance will be set at 0.05.

Vision and balance changes after bilateral implantation of Toric IOLs  
IRAS ID: 286913

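### Section 10.4 asks whether the Toric benefit varies with astigmatism but plans no arm-by-astigmatism test; judged band by band, a uniform benefit is likely to look band-specific

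*Combined protocol and SAP*

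**What the plan says.** Section 10.4 (Subgroup analyses) forms three bands in both arms. Mild is below 1.50 D, and the other two are given as "moderate (1.5-3.0) and severe (3.0" and above. The stated aim is "to help inform if Toric IOLs offer similar beneficial effect across cataract patients" with a wide range of astigmatism. The intended use follows directly: "This will help to identify which patients should be referred for Toric IOLs".

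The only method given is that outcomes in the bands will be compared. Section 10.4 names no test, interaction, multiplicity rule or exploratory label. It does not say which measure of astigmatism defines a band, or how a participant whose two eyes differ is placed.

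Nothing elsewhere fills the gap. In Section 10.3 the between-subjects factor is lens type and "the within-subjects factor would be time (pre-surgery vs post-surgery"). Sections 10.3.2 and 10.3.3 repeat the same mixed ANOVA. Astigmatism is not a term in any of these models.

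The sample size in Section 10.1 was derived "using mixed ANOVA (repeated measures, between factor being the type of IOL"), so it covers the overall comparison of lenses only.

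**The concern.** Whether benefit is similar across astigmatism depends on the difference between effects at different degrees of astigmatism. A significant result in one band beside a non-significant result in another does not measure that difference. It can arise when the true effect is identical in both, because each band holds only part of a sample sized for the whole.

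This is not the primary analysis, but it is the one the protocol links to patient selection. An apparent pattern produced by small bands could be carried into advice on referral.

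The bands also have practical faults. A value of exactly 3.0 D belongs to two of them. Section 6.1 admits corneal astigmatism from 1.00 D, while Section 6.2 excludes a predicted bilateral postoperative corneal astigmatism below 1.50 D, so the mild band may be nearly empty.

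**Working it through.** **Inputs from the documents.** Section 10.3: "Level of significance will be set at 0.05". Section 10.1: "With a power of 85% and level of significance" of 0.05; "an estimated medium effect size (0.25) will be used" (Cohen's f); 55 evaluable per arm; 20% dropout; 70 recruited per arm.

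**Assumptions, because the documents give no figure.** Number of measurements and their correlation in the sample size formula, band shares, and the distribution of astigmatism.

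**1. The plan's own figure.** For a repeated-measures ANOVA with a between factor, λ = f²·N·m / (1 + (m − 1)ρ). With m = 2 measurements and ρ = 0.5, λ = 0.0625 × 110 × 2 / 1.5 = 9.17. On 1 and 108 degrees of freedom this gives power 0.851. The stated 55 per arm is therefore reproduced under those two assumptions. Dropout: 55/0.8 = 68.75, so 69 per arm, against 70 stated.

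**2. Two effect sizes, in SD units.**
- 0.5 SD as a round value. With 55 per arm a two-sided 5% t test has 74% power, which is below the plan's 85%.
- The value that gives 85% overall: (1.960 + 1.036) × √(2/55) = 0.571 by the normal approximation, or 0.58 by the t test.

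**3. Power within one of three equal bands** (55/3, about 18 per arm):
- 0.5 SD, t test: 0.308.
- The 85%-power effect: 0.409 (normal approximation, 18.3 per arm) or 0.39 (t test, 18 per arm).
- Effect detectable with 85% power inside one band: 1.03 SD, against 0.58 SD overall.

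**4. Chance that the bands disagree on significance when the true effect is the same in all.** For three equal bands this is 1 − p³ − (1 − p)³.
- p = 0.308: 1 − 0.029 − 0.331 = 0.64.
- p = 0.409: 1 − 0.068 − 0.206 = 0.725 (0.71 with p = 0.39).

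For two equal bands of 27 per arm it is 2p(1 − p). With 0.5 SD, p = 0.438 and 2 × 0.438 × 0.562 = 0.49. The 85%-power effect gives nearly the same value.

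**5. Other band shares, with the 85%-power effect:**

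| Shares (mild/moderate/severe) | N = 110 | N = 140 |
|---|---|---|
| 1/3, 1/3, 1/3 | 72.5% | 75.0% |
| 40/40/20 | 73.7% | 76.9% |
| 50/35/15 | 75.1% | 79.2% |
| 20/60/20 | 76.2% | 80.5% |
| 10/70/20 | 79.0% | 84.5% |
| 0/70/30 | 55.2% | 52.7% |

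With equal thirds at N = 110, at least one band shows a reversed sign in 12% of trials. In 44%, the largest and smallest band estimates differ by at least the whole true effect. If there is no effect anywhere, three tests at 0.05 give 1 − 0.95³ = 14.3% chance of at least one false positive per outcome.

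**6. The interaction on the same footing.** In simulations of 20,000 trials with a uniform effect and three assumed distributions of astigmatism, the arm × continuous astigmatism term was significant in 4.95% to 5.2%.

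Its power when the effect does vary: the variance of the interaction slope per SD of astigmatism is about 4σ²/N, so z = k × 0.571 × √N / 2, where k is the change per SD as a fraction of the overall effect. For k = 0.5 and N = 110, z = 0.2857 × 5.244 = 1.50, and power is Φ(1.50 − 1.96) = 0.32.

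| k | N = 110 | N = 140 |
|---|---|---|
| 0.25 | 11% | 13% |
| 0.5 | 32% | 39% |
| 0.75 | 61% | 72% |
| 1.0 | 85% | 92% |

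**The case against.** The strongest reply is that Section 10.4 names no test. Comparing outcomes could mean tests within bands, comparison of bands within each arm, or a band factor added to the mixed ANOVA. That stands. A reader might infer that the plan commits to a separate significance test in each band, but the text does not say so, and the figures above apply only if bands are judged that way.

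Second, chance differences are likely rather than certain. With three equal bands and a 0.5 SD effect, no band is significant in about 33% of trials (0.692³), and then no band-specific claim arises.

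Third, a reader might infer that the trial would end up recommending referral for the wrong patients. The documents do not support that. Section 10.4 speaks only of helping to inform and to identify, and no rule ties a band's significance to referral.

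Fourth, the interaction is itself weak. It reaches 85% power at N = 110 only when the effect changes by the whole overall effect per SD of astigmatism. It would be wrong to present it as settling whether benefit is similar.

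Fifth, the 1.5 D cut has some basis in Sections 1 and 2, which say that people at or above it usually need spectacles or contact lenses, and the overlap at 3.0 D is a single shared value. Both are fair. They support keeping bands for description, but do not supply the missing comparison between bands.

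**Conclusion.** The concern holds in a limited form. The plan asks whether the effect varies with astigmatism and has no analysis that tests or estimates that variation. If bands are read separately, a uniform benefit would look band-specific in about 64% to 72% of trials with three equal bands, and in about half with two equal bands. Uneven three-band splits make this somewhat more frequent.

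These sizes rest on assumed band shares, a correlation of 0.5 in the plan's own formula, and a simple two-arm comparison within each band. The direction does not depend on any one scenario.

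The continuous interaction keeps the false-signal rate at about 5% and avoids the cut-points. It does not rescue the question: at this sample size only strong modification would be detected reliably. The change should be made, but the primary comparison is not affected.

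**What to change.** Rewrite the astigmatism part of Section 10.4 as one exploratory analysis:

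- **Outcome:** a single named primary dynamic stability measure at study visit 3. Section 3.4 lists angular position, velocity and acceleration across several activities, so one must be chosen or multiplicity across outcomes remains.
- **Model:** arm, baseline value of the outcome, preoperative corneal astigmatism as a continuous covariate, and arm × astigmatism, with a simple check for non-linearity.
- **Astigmatism value:** one per participant, defined in advance, for example the mean of the two eyes.
- **Reporting:** the Toric effect with 95% CI at chosen values within the enrolled range. Any statement on referral should rest on these estimates, not on which bands are significant.
- **Limitation to state:** power is about 32% at N = 110 for a half-effect change per SD of astigmatism, so a non-significant interaction does not show similar benefit.
- **Bands:** may stay for description if they do not overlap at 3.0 D. The mild band must be reconciled with Sections 6.1 and 6.2.

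The cost is SAP wording, a definition, and a small extra model that differs from the planned lens-by-time ANOVA. No new data are needed, since Appendix 2 already schedules astigmatism at screening and baseline. The downside is that a smooth trend is assumed, which the non-linearity check only partly guards against.
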